11.8 Pregnancy Reporting

Because of potential adverse effects on the fetus, pregnant subjects will be excluded from the study. Female subjects who are pubertal will be regularly assessed throughout the study. In the event of a test indicating the study subject is pregnant the subject will be informed of this result and will immediately have dexamethasone discontinued.

11.9 Clinical and Safety Monitoring

11.9.1 Subject Safety Monitoring

The DSMB (SMB, ISM) will be appointed by, and responsible to the NHLBI.

The DSMB will review a summary of the safety data for the study 6 months after the first subject is enrolled and every 6 months after that. A month prior to the scheduled meeting time, the SDMC will take all available data and generate a report of all relevant safety information (see above). Upon review of the safety data, the DSMB will make a recommendation to continue the trial or stop it due to safety concerns.

11.9.2 Clinical Monitoring Plan

A study coordinator will be appointed to assess the overall enrollment and compliance with the clinical protocol at all participating centers. Sites will be visited by a trained clinical monitor once every year for the duration of the trial. The monitoring will focus on data quality and provide feedback to the sites on how well they are capturing and entering data.

11.9.3 Plan for Reporting Protocol Violations

All protocol violations and deviations will be reported as soon as possible using the SDMC Deviation/Violation Form. This form will ask for a description of the event and what corrective action is planned.

12 DATA COLLECTION AND DATA MONITORING

12.1 CRF and Source Documentation

The site study coordinator will complete a CRF for each subject. A CRF manual will be provided to each site to assist in correct CRF completion. CRF data must be currently maintained and up-to-date.

Study participants must not be identified by name on any study documents. Subjects will be assigned and identified by CSCC subject numbers assigned at enrollment.

The specifics of source documentation maintenance will be detailed in the protocol manual of procedures.

12.2 Data Management

RhoFED's internet-based remote data entry system will be used to capture the data for this study. Using this system, clinical site personnel use an internet browser (Internet Explorer or similar) to key data into electronic CRF. The screens will be accessible via the CSCC website and require center-specific user ID/password privileges. Univariate data validation tests are performed as the data are keyed, and most implausible data values are resolved immediately. Data are not stored on the site's computer. At the end of each "page," data are submitted to RhoFED's secure web server using SSL (128 byte public key encryption methodology) and stored in the study's "operational database." (The database used for capturing, validating, updating, and storing the data is called an "operational database.") The database is backed up nightly; backup tapes are saved in a secure, off-site location. Authorized site personnel may log in to the system, review and correct previously entered data, key additional data, or lock records to prevent further inadvertent modifications at any time.

AEs will be coded at RhoFED using the MedDRA dictionary. AE codes will be entered into the operational database.

Approximately 1 month prior to each DSMB meeting RhoFED will take a “snapshot” of the operational database, create analysis datasets, perform statistical analyses, and prepare a DSMB report.

Upon completion of processing, the operational database is subjected to database closure procedures and subsequently locked.

After the operational database is locked, RhoFED’s programming team will create and validate an analysis database. The analysis database will be the basis for statistical analyses of the data.

12.3 Staff Training

Prior to the onset of enrollment, clinical study coordinators and data coordinators will be centrally trained to ensure adherence to the protocol and assure the highest possible data quality. Training will be led by a combination of investigators and other staff from the clinical centers, the SDMC, and NHLBI. Training presentations will address informed consent procedures, study operations and protocol requirements, data collection procedures, maintenance of source documentation, CRF completion and review, routine reporting requirements, data entry and management, and CSCC and NHLBI policies and procedures. As needed and as time allows, face-to-face training will be provided by SDMC staff as part of periodic site visits.

12.4 Data Monitoring

After central training, individual sites will monitor CRFs and source documents for accuracy, protocol compliance, subject safety, and adherence to guidelines.

As referenced above, centers will be site-visited. At each site visit, recruitment guidelines and study eligibility criteria will be reviewed. As the study progresses, completed data forms may be reviewed during site visits and compared to source documentation (medical or center records) to confirm accuracy.

13 STATISTICAL ANALYSIS

Analyses will be prospectively described in a Statistical Analysis Plan (SAP). Additional statistical procedures may be used if necessary (e.g., data transformations). In general, data will be summarized by treatment and age group using univariate statistics (e.g., N, mean, standard deviation, median, minimum, and maximum) or frequency (e.g., N, percentage), as appropriate.

13.1 Analysis Populations

The general population will consist of hospitalized subjects 5 years of age and older with a diagnosis of SCD, who have experienced a current episode of ACS and who have provided a written informed consent. Randomized subjects who are not dosed will be replaced. Data collected on subjects who do not complete the study will be used whenever possible. The exact criteria used to establish each analysis population and any predefined reasons for eliminating subjects will be identified and documented before the study is unblinded.

Intent-to-Treat (ITT) / Safety population: All randomized subjects will be included in the ITT/Safety population. Subjects in the ITT population will be classified according to the treatment group to which they were randomized regardless of what study drug they received.

Per-Protocol population: The per-protocol population consists of all subjects from the ITT/Safety population who had no major protocol violations and who were followed until discharge from the study.

All analyses will be performed on the ITT population. Efficacy analyses will be repeated on the per protocol population.

13.2 Statistical Methods

13.2.1 Study Population

Descriptive summaries will be generated to describe the disposition of all enrolled subjects. Descriptive summaries will also be generated for all relevant baseline variables

by age strata, severity strata, and treatment group. These variables include, but are not limited to, demographic data, medical history, and study populations.

13.2.2 Efficacy Analyses

All efficacy analyses will be performed on the ITT population while the primary and some secondary analyses will be repeated on the per-protocol population. Center will be included in the models as permitted by sample size. Center will be eliminated from the models if it appears to be an insignificant variable in the model.

The primary analysis will compare the duration of ACS signs and symptoms (as assessed by the ACS assessment, Appendix3) or the duration of hospitalization for ACS, whichever happens first, of subjects in the dexamethasone treated arm to those in the placebo treated arm. The symptom/hospitalization duration for subjects with ACS will be summarized by treatment group, severity strata, and age strata. The effect of treatment on symptom/hospitalization duration will be tested using a Generalized Linear Mixed Model (GLMM) with the natural log of symptom/hospitalization duration as the outcome variable. The SAS[®] procedure MIXED will be used to fit the GLMM. The GLMM will include treatment, age group, and severity as fixed effects. The GLMM will not specify any variables as random effects or repeated effects, but it will use the GROUP option in the REPEATED statement to estimate separate error variances for each treatment (i.e., GROUP = “treatment”). The SAS[®] procedure MIXED will be used to fit the GLMM.

The GLMM model specified above is necessary for the primary analysis because pilot data give evidence that the length of stay (LOS) in the hospital (which is assumed to be similar to duration of symptoms) for ACS has a lognormal distribution. If the LOS for ACS is distributed as lognormal in each treatment group, then the model of the natural log of LOS must allow for differences in treatment group variances as well as for treatment group mean differences. By allowing for differences in treatment group variances and treatment group means, the treatment group specific distributions can be correctly estimated under the lognormal assumption, resulting in a correct comparison of treatment group means.

As a secondary analysis, parametric survival analysis techniques will be used to estimate distributional parameters and model the hazard function of symptom duration/LOS/hypoxemia/fever for each treatment group. The time to the event of interest (e.g., symptom duration) will be described using a Kaplan-Meier plot stratified by treatment.

The effects of dexamethasone on secondary clinical endpoints of duration of hospitalization, supplemental oxygen therapy (or hypoxemia), and fever will be summarized by treatment group, severity strata, and age strata and evaluated by using a similar GLMM as the primary analysis. The secondary clinical endpoints of the amount of opioid usage, the number/type of transfusions, pulmonary function and pulmonary radiograph findings, the number of rebound hospitalizations, and pain scores, will be summarized by treatment group, severity strata, and age strata. The effects of dexamethasone treatment on these outcome variables will be evaluated using:

- GLMM with treatment, age group, severity, and timepoint as fixed effects and subject as a random effect for the longitudinal pain scores;
- Wilcoxon Rank test for rebound hospitalizations and number of transfusions;
- T-Test (or Wilcoxon Rank test if assumptions are not met) for the amount of opioid usage and all pulmonary function outcomes;
- Cochran-Mantel-Haenszel Chi-square test for radiographic findings (resolved, improved, unchanged, worse).

The secondary endpoints of the laboratory variables (VCAM₁, ICAM₁, P-selectin, L-selectin, vWF multimers, endothelial and monocyte microparticles, WBTF, NO, and sPLA₂) will be summarized by measurement timepoint, treatment group, severity strata, and age strata. The overall change from baseline for each of the collected measurements over time will be modeled using a random effects longitudinal mixed model, with treatment, baseline measurement, age group, and severity as fixed effects and subject as a random effect. This class of model allows us to control for the correlation induced by having multiple measurements on an individual. Estimates of the treatment difference over time will be depicted by displaying the estimated means of each treatment group over time. Descriptive p-values for comparisons of interest will also be produced.

All meaningful subject data collected in the CRFs will be provided in data listings. All statistical analyses will be performed using the SAS[®] System.

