9.2 Randomization and Masking

After enrollment, subjects will be randomized to one of two treatment arms. Subjects in Arm 1 will receive oral dexamethasone. Subjects in Arm 2 will receive oral placebo. A computer-generated, adaptive randomization schema will be used to allocate subjects 1:1 between the two treatment arms. Randomization will be stratified by site, age and the severity of ACS (see Section 8.3). In order to increase the likelihood of balance in treatment allocations, subjects will be randomized using the standardized range variation (79) of the sequential allocation algorithm of Pocock and Simon (80), a minimization method. This method attempts to achieve treatment balance on several subject characteristics (i.e. age group, site, and severity of ACS in this study) simultaneously – not within separate strata. Minimization consists of biasing the treatment allocation so as to minimize the total imbalance between the treatment groups on some scale (81). The order of entry of the subjects to the various centers and in the various prognostic groups is assumed to be random. As minimization is a dynamic method that uses information on subjects already entered to allocate treatment to the next subject, a continuous updating of the information related to previous treatment allocations is required, thus a centralized randomization system will be used.

Pharmacists at each center will be unblinded and will utilize information from the interactive voice/web randomization system (IVRS) at the SDMC to obtain a new treatment assignment for a subject and provide each subject with appropriate dosing of both therapies. The IVRS system has the capability of providing unblinding information in case of a medical emergency where the exact study drug is needed in order to appropriately treat a subject.

The time interval between Randomization and the first dose of study drug administration will be no longer than 2 hours. In the event a subject's first dose occurs outside the 2-hour time limit, the subject will still be included in the study and the analysis. This is in the spirit of the intention-to-treat analysis. The amount of time in excess of the 2-hour limit until the first dose of study drug will also be recorded. This event will be documented as a protocol deviation.

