13.3 Statistical Considerations

13.3.1 Covariates

Age group and severity group will be used as covariates in the primary analysis. Baseline laboratory measurements will be controlled for when analyzing laboratory outcomes. Center will be included in the models as permitted by sample size. Other covariates may be considered in the analysis of clinical, laboratory, and safety outcomes as needed.

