13.3.2 Multi-center Studies

Randomization will be stratified by severity group, center and age group to preserve a balance across treatment groups. Center effects will be examined as permitted by sample size.

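### Site is a minimization factor, but the protocol does not settle whether it is in the primary model and lets outcome data decide

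*Protocol*

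**What the plan says.** **Allocation.** Protocol Section 9.2 describes 1:1 allocation by minimization and names the balancing factors: "i.e. age group, site, and severity of ACS in this study". Section 13.3.2 restates this: "Randomization will be stratified by severity group, center and age group to preserve a balance across treatment groups".

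**Center in the models.** Section 13.2.2 opens with two sentences on the efficacy models generally: "Center will be included in the models as permitted by sample size", then "Center will be eliminated from the models if it appears to be an insignificant variable in the model". Neither gives a criterion.

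**The primary model.** The next paragraph of Section 13.2.2 says: "The GLMM will include treatment, age group, and severity as fixed effects". It adds that the model has no random effects and has a separate error variance per arm. Section 13.3.1 says: "Age group and severity group will be used as covariates in the primary analysis", then repeats the sample-size clause for center.

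**Looks.** Section 13.2.4 plans analyses at 56 subjects (p < 0.001), at 112 subjects (0.01 overall, 0.05 in children) and after 112 children (0.039). It applies the primary-analysis F-test at the first look and states that overall alpha stays at 0.05.

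**The concern.** Whether center looks unimportant can be known only by fitting the outcome model. Two primary p-values are then available, with no stated rule for choosing between them. Nothing prevents center from being out at 56 subjects and in later, so successive stopping boundaries could be applied to different tests. The claim in Section 13.2.4 that alpha is preserved presupposes one defined test.

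Site is also a plausible source of variation. Section 9.1.6 leaves discharge to the treating physician, and under Section 7.1.1 and Appendix 3 discharge ends the primary duration. With few subjects per site, a non-significant site test is weak evidence that sites are alike.

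At stake are the pre-specification of the primary test and, if site is left out while it matters, some of the precision that balancing on it provides.

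**Working it through.** **1. The protocol's own figure.** Section 13.4 assumes SDs of ln(LOS) of 0.6 and 0.3, means of 4.25 and 3.95, two-sided alpha 0.05 and 90% power. Normal formula: (0.6² + 0.3²)(1.960 + 1.282)² / 0.30² ≈ 52.5, so 53 per arm. Exact Satterthwaite power is 89.5% at 53, 90.07% at 54 and 91.1% at 56. The stated 54 (56 with withdrawals) reproduces. The implied mean difference is exp(4.25 + 0.18) − exp(3.95 + 0.045) = 83.9 − 54.3 = 29.6 h, against the stated 30 h.

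**2. Simulation set-up.** 4,000 trials per setting; minimization on site, age and severity; ln(duration) fitted with one variance per arm; difference 0.30 or 0. *Assumed, not in the protocol:* 6, 12 or 20 sites; between-site SD of ln(duration) from 0 to 0.3 (an SD of 0.2 is a factor of exp(0.2) = 1.22 in duration); biased coin 0.8; 33% adults; 25% severe; drop threshold p ≥ 0.05. The total of 112 at 0.05 matches the sample-size calculation, not the alpha of any planned look. Monte Carlo error at 5% is √(0.05 × 0.95 / 4,000) = 0.34 points.

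**3. Results at N = 112 (%).** Each triple is center always in / always out / dropped by rule.

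| Sites, site SD | Center kept by rule | Type I error | Power | In and out disagree (design effect) |
|---|---|---|---|---|
| 6, 0.1 | 39 | 5.7 / 5.4 / 5.5 | 91.0 / 90.7 / 91.2 | 1.9 |
| 6, 0.2 | 83 | 5.7 / 4.7 / 5.6 | 91.0 / 88.5 / 90.9 | 3.5 |
| 6, 0.3 | 95 | 5.7 / 3.9 / 5.7 | 91.0 / 85.0 / 91.0 | 6.8 |
| 12, 0 | 7 | 5.6 / 5.5 / 5.6 | 90.7 / 91.5 / 91.6 | 2.5 |
| 12, 0.2 | 85 | 5.2 / 4.2 / 5.3 | 90.5 / 88.3 / 90.6 | 5.0 |
| 12, 0.3 | 98 | 5.2 / 3.4 / 5.2 | 90.5 / 83.6 / 90.4 | 8.9 |
| 20, 0 | 7 | 4.8 / 4.9 / 5.0 | 88.7 / 91.8 / 91.7 | 4.4 |
| 20, 0.3 | 98 | 4.9 / 3.4 / 4.9 | 88.4 / 82.1 / 88.5 | 10.1 |

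- *Rule applied mechanically:* type I error 4.9-5.7%, power 88-92%, close to always keeping center (4.8-5.7%, 88-91%). A second simulation (8 or 14 sites, balance within site, 20,000 trials per setting) gives 4.8-5.0% under the rule and a power loss of at most about 0.3 points.
- *Choice left open:* the two analyses disagree in 1-2.5% of null trials and 1-10% of trials with the design effect. Taking the smaller p-value rejects a true null in 5.6-6.5% (6 or 12 sites).
- *Center out regardless, site SD 0.2-0.3:* type I error 3.4-4.7%, power 82-89% against 88-91% with center kept.

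**4. Between looks.** At site SD 0.2, the rule drops center in 38% of trials at 56 subjects and 17% at 112 with 6 sites; with 12 sites, 44% and 15%. The model tested can thus change with sample size alone. At the 56-subject look with alpha 0.001 and the design effect, the two analyses disagree in 3.0-7.7% of trials.

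**The case against.** **Read literally, the primary model contains no center.** The model statement in Section 13.2.2 and the covariate sentence in Section 13.3.1 name only age group and severity, and the interim F-test refers to that model. On this reading there is no choice to make. But the opening sentences of Section 13.2.2 cover the efficacy models without excepting the primary one, and Section 13.3.1 repeats the sample-size clause straight after its covariate sentence. The contradiction stands. If the literal reading were intended, a balancing factor would always be omitted, which is the conservative case above.

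**A reader might infer that dropping center under this rule gives error bars that are too wide.** The documents do not support that. Overstated standard errors come from omitting site while sites differ, and this rule omits it only when it looks unimportant. In trials where center was dropped at N = 112, the standard error without site was 0.96-1.00 times that with site. In the second simulation it was 1.2-2.5% larger, with type I error of 3.6-4.3%. Larger overstatement (mean standard error 1.11-1.20 times the true SD) appeared only at site SD 0.3 with 12 or 20 sites, where about 2% of trials drop center.

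**A reader might also infer that the rule inflates type I error.** Applied at one fixed threshold, it does not do so to a meaningful degree. A change of model between looks is left open by the text, not stated in it.

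**This could be left to the SAP.** The SAP is not at hand and may settle the matter. The protocol nevertheless states an elimination rule, and a SAP that follows it inherits the problem.

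**Conclusion.** The concern holds as a defect of pre-specification. The protocol is inconsistent on whether center belongs in the primary model, and its removal rule depends on outcome data without a test or threshold. Under a mechanical 0.05 rule the effect on type I error and power is small. What matters is the discretion between two analyses, and the loss of up to about 6 points of power (88.4% to 82.1% with 20 sites at site SD 0.3; 12 sites similar) if center is left out, for example on the undefined sample-size ground, while sites differ. All magnitudes depend on assumed site numbers, between-site SD and drop threshold, none of which the protocol gives. This is a low-severity point that is easily corrected.

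**What to change.** 1. In Section 13.2.2, delete the elimination sentence.
2. State one primary model for every look: treatment, age group, severity and site as fixed effects, keeping the separate error variances.
3. In Sections 13.2.2 and 13.3.1, replace the sample-size clause with a rule, set before unblinding, for pooling small sites. Add site to the covariate sentence in Section 13.3.1.
4. If a random site intercept is preferred, also amend the statement in Section 13.2.2 that the model has no random effects. The simulations above used fixed site effects, so they do not evaluate that option.
5. Report the model without site as a sensitivity analysis.

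The cost is a few sentences and no patients or data. The statistical price is one degree of freedom fewer than the number of site groups. If sites do not differ at all, keeping them costs about 0.8 points of power with 12 sites (91.5 − 90.7) and 3.1 with 20 (91.8 − 88.7). Pooling small sites reduces the number of site terms.

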7 STUDY DESIGN

7.1 Description of Study Design

7.1.1 Description Of Primary And Secondary Endpoints

The *primary endpoint* is the duration of signs and symptoms of ACS or the duration of hospitalization, whichever is less. The duration of signs and symptoms of ACS is defined as the interval between first dose of study drug and the time at which the elements of the ACS assessment are satisfied. The ACS assessment incorporate assessments of tachypnea, hypoxemia, work of breathing, thoracic pain, and medical interventions to support respiration (Appendix3). The elements of the ACS assessment will be formally assessed and recorded every 4 hours until discharge from the hospital.

The *secondary endpoints* include the following:

- Amount and type of opioid used;
- Number and type (simple or exchange) of transfusions received;
- Duration of Supplemental oxygen;
- Duration of hospitalization;
- Duration of fever;
- Duration of hypoxemia;
- Rebound hospitalizations;
- Results of pulmonary function testing (FVC, FEV₁, FEF_{25-75%}, PEFR, and flow-volume loop);
- Pulmonary radiographic findings (resolved, improved, unchanged, and worse); and,

- Rating of pain [Oucher or numeric rating scale (both are 0-10 scales)].

The *safety endpoints* include the following:

- Vital signs, including blood pressure;
- Physical examination;
- Urine output and daily fluid balance;
- Blood culture (for fever);
- CBC;
- Reticulocyte count;
- Peripheral oxygen saturation by pulse oximetry;
- AE monitoring;
- Baseline history and interim history (including pain history, pain treatment, respiratory symptoms, inpatient or outpatient evaluations, and management of SCD-related complications); and,
- Concomitant medications monitoring.

The *laboratory endpoints* include the following:

- Plasma soluble biomarkers (VCAM-1, ICAM-1, P-selectin, L-selectin and vWF multimers);
- Flow Cytometry for endothelial microparticles (VCAM₁ and TF) and monocyte microparticles (TF);
- Nitric Oxide metabolites;
- Whole blood tissue factor (WBTF)
- SPLA₂

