8.1 Inclusion Criteria

Subjects who meet all of the following criteria are eligible for enrollment into the study:

1. Age \geq 5 years;
2. Diagnosis of sickle cell anemia (Hgb SS) or sickle- β^0 -thalassemia (Hgb S β^0);

3. Current episode of ACS defined as a new lobar or segmental pulmonary infiltrate seen on a chest radiograph and two or more of the following findings in the 24 hours preceding enrollment (signing consent):
 - temperature $\geq 38.5^{\circ}\text{C}$,
 - tachypnea,
 - dyspnea or increased work of breathing,
 - chest wall pain, and
 - oxygen saturation of $< 90\%$ in room air by pulse oximetry;
4. Subjects must have one or more of the following findings at the time enrollment:
 - tachypnea,
 - dyspnea or increased work of breathing,
 - chest wall pain, and
 - oxygen saturation of $< 90\%$ in room air by pulse oximetry;
5. Current episode of ACS diagnosed within the preceding 24 hours;
6. Ability to take medication in capsule form;
7. Written, informed consent provided by the subject and/or parent(s) or guardian(s) before study entry.

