10.3 Evaluations by Study Visit

10.3.1 Baseline Evaluations

A chest radiograph is necessary for the diagnosis of ACS, the medical care of the subject, and study enrollment. Immediately after enrolling a subject, the elements of the ACS assessment will be assessed and the following additional assessments performed or measurements taken: history (which includes the collection of any transfusions within 24 hours of enrollment), physical exam, vitals signs (includes blood pressure monitoring), a CBC, blood culture (for those subjects with fever), a pregnancy test if applicable, pain intensity (by Oucher or numeric rating scale), and peripheral oxygen saturation (by pulse oximetry) [See Table 10.2.] Additionally, a blood sample will be drawn for the central laboratory measurements (see Table 10.1).

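### The primary model omits the baseline ACS Assessment, the starting state of its own endpoint, at a modest and conditional cost in precision

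*Protocol*

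**What the plan says.** Protocol 13.2.2 fixes the primary model for the natural log of symptom/hospitalization duration: "The GLMM will include treatment, age group, and severity as fixed effects". Section 13.3.1 repeats it: "Age group and severity group will be used as covariates in the primary analysis". Center enters as sample size permits and is dropped if it appears insignificant. Section 13.3.1 also has an open clause, "Other covariates may be considered in the analysis of clinical, laboratory, and safety outcomes as needed", which names no variable. For the biomarkers it does commit to baseline adjustment: "Baseline laboratory measurements will be controlled for when analyzing laboratory outcomes".

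Section 7.1.1 defines symptom duration as the "interval between first dose of study drug and the time at which the elements of the ACS assessment are satisfied", and the endpoint is the shorter of that and the hospital stay. Appendix 3 lists the five elements: respiratory rate, work of breathing, thoracic pain, room-air saturation, and medical intervention (oxygen or ventilatory support).

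Section 10.3.1 collects the same elements at the start: "Immediately after enrolling a subject, the elements of the ACS assessment will be assessed". Table 10.2 marks the assessment at Baseline. Inclusion criterion 4 (section 8.1) reads "Subjects must have one or more of the following findings at the time enrollment" and lists tachypnea, dyspnea or increased work of breathing, chest wall pain, and low saturation.

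**The concern.** Subjects who start with more elements unresolved, or with worse values on them, have further to go before the endpoint is met. If that predicts log duration beyond age group and severity, the primary model leaves explainable variation in its error term.

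Severity (section 8.3) is a partial substitute. It has two levels, set by saturation below 85% (or at most 90% on maximal oxygen), three or more lobes, or impending or actual need for ventilatory support. Work of breathing enters only indirectly, through impending respiratory failure. Respiratory rate, the thoracic pain score, ordinary supplemental oxygen and graded saturation are not in it. A subject with mild chest pain alone and one with tachypnea, retractions, severe thoracic pain and a saturation of 87% can both fall in the mild-to-moderate stratum.

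Minimization (section 9.2) acts on site, age group and severity, so it does not directly balance starting state, and the model does not adjust for a chance imbalance in it. What is at stake is power at the interim and final tests, using data the trial already collects.

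**Working it through.** **Range of starting states.** Criterion 4 lists findings, not Appendix 3 elements. Chest wall pain of any score, or dyspnea alone, qualifies. Appendix 3 counts thoracic pain of 4 or less as met and does not score dyspnea. A subject can therefore enter with no element unmet, and the possible range is 0 to 5.

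**The plan's own figure (section 13.4).** Inputs: log means 4.25 and 3.95 (difference 0.30), SDs 0.6 (placebo) and 0.3 (dexamethasone), two-sided alpha 0.05, Satterthwaite t-test, equal n.

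- SE = √[(σ_P² + σ_D²)/n]; noncentrality λ = 0.30/SE; Satterthwaite df = (n − 1)(σ_P² + σ_D²)²/(σ_P⁴ + σ_D⁴); power from the noncentral t.
- n = 54: SE = √(0.45/54) = 0.0913, λ = 3.286, df = 77.9, power 90.1%. The stated 54 per arm reproduces.
- n = 56, alpha 0.05: power 91.1%.

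**Effect of one baseline covariate.** A single linear term has one slope for both arms, so it removes the same absolute variance c from each. Let ρ_D be the assumed correlation in the dexamethasone arm, beyond age group and severity. The planning SDs are taken as the residual SDs.

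- c = ρ_D² × 0.09; the implied placebo correlation is √(c/0.36) = ρ_D/2.
- ρ_D = 0.3: c = 0.0081; variances 0.3519 and 0.0819; SE × √(0.4338/0.45) = 0.982; placebo correlation 0.15.
- ρ_D = 0.5: c = 0.0225; variances 0.3375 and 0.0675; SE × √(0.405/0.45) = 0.949; placebo correlation 0.25.

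The alpha levels come from section 13.2.4. Section 7.1.2 gives up to 112 children and an anticipated maximum of 56 adults, so a final test on everyone could have (112 + 56)/2 = 84 per arm.

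| Test | No baseline term | ρ_D = 0.3 | ρ_D = 0.5 |
|---|---|---|---|
| 56 per arm, alpha 0.039 | 89.2% | 90.3% | 92.1% |
| 56 per arm, alpha 0.01 (second interim, all subjects) | 75.9% | 77.7% | 80.9% |
| 84 per arm, alpha 0.039 | 97.7% | 98.1% | 98.7% |

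The gains are 1.1 to 2.9 points, 1.8 to 5.0 points, and 0.4 to 1.0 point.

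**Cost of the term.** With about four parameters already fitted, one more breaks even when it explains roughly 1/(N − 4 − 2) of the residual variance: 1/106 = 0.9% at 112 subjects, and 1/50 = 2% at 56.

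**The case against.** The strongest reply is that nothing here is wrong. The model is prespecified and valid, it adjusts for two of the minimization factors, and the sample size is correct without further adjustment. A separate analysis plan may add detail, and 13.3.1 leaves room for other covariates. Most of this stands, and it limits the point to efficiency. The open clause does not settle it, because it commits to nothing while both sections name the primary covariates outright.

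Two further objections also have force. First, Appendix 3 defines no total score. A simple count touches oxygenation twice (saturation and supplemental oxygen) and overlaps with severity, so the count is one reasonable form among several. Second, the biomarker comparison is loose: a biomarker has a baseline value of itself, whereas a duration does not.

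A reader might infer a much larger gain by shrinking both variances by the factor 1 − ρ². At 56 per arm and alpha 0.039, ρ = 0.5 would then give 96.0%. With SDs of 0.6 and 0.3 this needs a slope twice as steep on placebo, which a single common term does not have. Reaching about 96% with a common slope needs a dexamethasone-arm correlation near 0.79. Pairing SDs of 0.6 and 0.5 with the 0.30 log difference is also tempting, but it implies exp(4.43) − exp(4.075) = 83.9 − 58.9 = about 25 hours. That falls short of the 30-hour minimum in section 13.4, so it is not a scenario the protocol claims to cover.

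**Conclusion.** The point holds as a modest, avoidable loss of precision. The omission is plain in 13.2.2 and 13.3.1, the data are collected before dosing, and severity covers only part of the starting state. Its size cannot be settled from the protocol, which reports no correlation. The figures assume a common slope, the planning SDs as residual SDs, and correlations of 0.3 to 0.5 (dexamethasone) and 0.15 to 0.25 (placebo) beyond age group and severity.

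On that footing the gain is about 1 to 3 points at 56 per arm and alpha 0.039, and about 2 to 5 points for the all-subject test at the second interim, where stopping also requires significance in children. The first of these applies only if the final test has 112 subjects in total; with 84 per arm the gain is about one point or less.

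A reader might infer that the treatment comparison is biased, that type I error is inflated, or that 56 per arm is too few. The documents support none of these. Randomization protects the unadjusted comparison, and the stated sample size reproduces without the extra term.

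**What to change.** In 13.2.2 and 13.3.1, add the baseline ACS Assessment as a fixed covariate in the primary GLMM, in its interim tests and in the duration-of-hospitalization model, keeping age group and severity. One workable form is the number of Appendix 3 elements not met at the enrollment assessment (0 to 5, linear). Whichever form is chosen must be fixed before unblinding and before the first interim, since 13.2.4 uses the same F-test there. The cost is a line in each section and one degree of freedom, with no new data.
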